## ii. List of Abbreviations

BI	Business Intelligence (Yorkshire Ambulance Service)
CAG	Confidentiality Advisory Group
CI	Chief Investigator
CiCS	Corporate Information and Computing Services (University of Sheffield)
CURE	Centre for Urgent and Emergency Care Research (University of Sheffield)
DOLS	Deprivation Of Liberty Safeguards
DSA	Data Sharing Agreement
ECDS	Emergency Care Data Set (NHS Digital)
ED	Emergency Department
ePCR	Electronic Patient Care Record (Yorkshire Ambulance Service)
EPV	Events Per Variable (aka Events Per Parameter)
FAST	Face, Arms, Speech, Time
GCP	Good Clinical Practice
HRA	Health Research Authority
ICMJE	International Committee of Medical Journal Editors
IMD	Index of Multiple Deprivation
LASSO	Least Absolute Shrinkage and Selection Operator
LOESS	Locally weighted Scatterplot Smoothing
LSOA	Lower Super Output Area
NACN	National Ambulance Commissioners Network
NEWS	National Early Warning Score
NHSD	NHS Digital
NIHR	National Institute of Health Research
NPV	Negative Predictive Value
PPV	Positive Predictive Value
RDS	Research Design Service
ROC	Receiver Operating Characteristic
SCHARR	School of Health and Related Research (University of Sheffield)
SECF	Sheffield Emergency Care Forum
SHARRP	Sheffield Addiction Recovery Research Panel
SINEPOST	Safety Index of Prehospital On Scene Triage
SNOMED CT	Systematized Nomenclature of Medicine Clinical Terms
UECRT	Urgent and Emergency Care Review Team
UOS	University of Sheffield
VM	Virtual Machine
YAS	Yorkshire Ambulance Service

### iii. Study Summary

Study Title	The Safety Index of Prehospital On Scene Triage: The derivation and validation of a risk prediction model to support ambulance clinical transport decisions on scene.
Internal ref. no. (or short title)	The SINEPOST study.
Study Design	Risk prediction modelling on linked healthcare data.
Study Participants	Adult (over the age of 18) ambulance service patients attended by Yorkshire Ambulance Service between July 2019 and December 2019.
Planned Sample Size	466,846
Planned Study Period	September 2019 – June 2021

	Objectives	Outcome Measures
Primary		
Can ambulance service clinical data predict an avoidable attendance at the ED in adults using classification models?	To build classification models deriving risk predictions using prehospital clinical data as input variables, and ED experience as the output variable.	ED experience (avoidable/non-avoidable)
Secondary		
What is the simulated transportability of the model derived from the primary outcome?	Internally validate the model and apply to a retrospective cohort of non-conveyed patients.	ED experience (avoidable/non-avoidable)
Which classification model is most accurate at predicting an avoidable attendance at the ED in adults?	Compare the different classification models for most accurate and feasible to embed in practice.	Comparative accuracy in prediction, misclassification rate, imprecision and inaccuracy.

#### v. Role of study sponsor and funder

Yorkshire Ambulance Service NHS Trust (YAS) is the sponsor of this study as the employer of **the student investigator**. Yorkshire Ambulance Service will undertake all sponsor responsibilities outlined the UK Policy Framework for Health and Social Care Research.

The National Institute of Health Research (NIHR) Academy are the funder of this study. They will undertake all funder responsibilities outlined in the UK Policy Framework for Health and Social Care Research.

#### vi. Roles and responsibilities of study management groups & individuals

There will be no Study Management Committees

#### viii. Key words

[figure not shown]
Risk Prediction, Ambulance Service, Discharge on scene, Data linkage, Modelling

# ix. Study flow chart

## DATA FLOW DIAGRAM OF DATASET PREPARATION AND LINKAGE

## DATA FLOW DIAGRAM OF DATASET USAGE

# 1 Background

## *The demand problem*

Demand for the urgent and emergency care system is increasing (~5.2% annually). 10.7 million calls were transferred to the ambulance service with 6.6 million receiving a face-to-face attendance. The vast majority of these calls were urgent and not emergencies. This demand is also mirrored in ED, which results in delays when the ambulance service is handing the patient over. In a 3 month winter period in 2017/18 in England, there were 41,879 patient episodes where an ambulance took over an hour to handover to the ED. There is international evidence from the USA, Canada, UK and Australia showing ambulance ramping can be both a consequence and a cause of ED crowding. Queuing ambulances means less resources are available to respond to 999 calls, which has a damaging effect on patient care and ambulance service performance. Furthermore, the accuracy in the decision to convey a patient to the ED is not always accurate. A 2018 study found that up to 16.9% of ambulance conveyances to the ED were potentially avoidable. This study used a process-based validated definition of avoidable, which is being used in this project as the primary outcome measure.

More evidence is required in identifying patients who are likely to have an avoidable conveyance to the ED, whilst they are still with the ambulance service on-scene.

## *The case-mix problem*

The majority of ambulance service patients require less critical interventions and more community based care. In response to this, policy has been driving paramedics to make autonomous and dynamic decisions about their patient care before transporting them to the ED. This theme was particularly emphasised in the Urgent and Emergency Care Review Team (UECRT) report in 2013. One of the main outcomes they aimed to achieve in the report were for those with an urgent need to access healthcare be provided with a highly responsive, effective, and personalised service outside of hospital.

Interventions have been developed to stratify patient risk on-scene and decide where the best care of a patient should be. One example that has been adopted by numerous ambulance services is the paramedic pathfinder tool. The tool was user tested in 2014 when a sample of 481 patients had the tool applied to them with results showing sensitivity of 94.83% and specificity of 57.9%. The tool was highly risk averse with almost half of the patients being transported to the ED, when the care could have safely been elsewhere. Furthermore, O Hara et al. used qualitative methods to conclude that paramedic decision making is multifactorial and complicated. They emphasised a decision not to transport a patient was the most challenging.

More evidence is required to risk stratify patients and allow paramedics to make more discriminate ED transport decisions on-scene.

# 2 Rationale

This research is supporting paramedics to make more appropriate and effective decisions for patients who may not require the level of care provided by a hospital. It is important as it is aiming to navigate care decisions that will safely provide patients with the right care, first time. If a paramedic can see the likelihood that their patient may have an avoidable attendance, it opens up an opportunity to explore community options. It also empowers the patient to be an active partner in developing a self-care plan. The whole urgent and emergency care system would benefit from this research. If paramedics can make safe non-transport decisions it frees their capacity to assess a patient still waiting for help. With less patients being transported to the ED with low acuity problems, it will minimise delays in caring for those who do need specialist ED interventions. For community care it will identify patients that require out of hospital services so that they can get the right level of care promptly. This project does recognise when a paramedic assesses a patient, there are six possible outcomes relating to a transport decision. Firmer evidence surrounding outcome measures for the other five dispositions is needed before tools that can accurately signpost patients to any service can be developed.

## Review of existing evidence

### *Paramedic decision making*

In 2014, O'Hara et al. published a qualitative report on paramedic decision making in transitioning care. It appears to be the most comprehensive exploration on the subject to date. They identified the most complex type of decision surrounds non-conveyance and the concept of discharging the patient on-scene. This conclusion agrees with many other sources. A cause of this complexity is the perception of job role as illustrated by Hoikka et al. They elude to paramedic education being focussed on high acuity situations, which foster a culture that could struggle in recognising and discharging low acuity patients. Simpson et al. also demonstrated that role perception was crucial in the decision-making process of paramedic's on-scene. They undertook a qualitative study with thirty-three paramedics examining decision-making in the elderly who have fallen. They acknowledged that role perception was profound on how a paramedic approaches a decision. This idea is reaffirmed by Brydges et al. who state:

*"Many of the participants perceived their role as a paramedic to be defined by responding to emergency calls for help (i.e., consistent with their initial education and certification expectations), and referral programs represented a formal departure from that enduring view." (p. 633)*

### *Non-conveyance*

Non-conveyance can be defined as "an ambulance deployment as appropriate, where the patient after examination and/or treatment on-scene does not require conveyance with medical personnel and equipment to the healthcare facility". Ebben et al. produced a recent systematic review on the subject; focusing on patient safety and outcomes further along in the patient journey. This systematic review appears to be the most comprehensive in comparison to other reviews undertaken in the same subject area. Sixty seven studies were included in the review with the majority being quantitative observational studies. The rate of non-conveyance varied between 3.7%–93.7%. This was due to the differences in prehospital models between countries.

According to NHS England, the current non-conveyance rate experienced nationally in the UK is 37.6% (locally in Yorkshire it is 30.6%). The limitation of this report is that the data collected is used as a performance measure for the ambulance service. This could introduce a bias into the data collection stage and mar the accuracy of the report. A different approach to non-conveyance would be to ascertain clinical necessity of conveyance. Patton and Thakore found that a third of their sample attended the ED 'inappropriately' although their sample size was low (n=295).

### *Decision tools*

There is currently a lack of evidence to support the use of tools to assist in prehospital decision making regarding the need to transport the patient to the ED. Conversely, tools used within the ED to risk stratify patients and predict admission have demonstrated high accuracy. Cameron et al. compared two admission prediction tools: the Glasgow Admission Prediction Score (GAPS) and Amb Score. They found the Area Under Curve (AUC) of 0.807 (95% CI 0.785-0.830) for GAPS and 0.743 (95% CI 0.717 to 0.769) for the Amb Score. These were derived using multivariable logistic regression. Advances in technology, in particular electronic health records has enabled complicated predictive models to support the clinician in making more discriminate decisions. Levine et al. used random forest modelling to triage patients entering the ED and compared this with the Emergency Severity Index (ESI). They found the random forest was more accurate at stratifying mid-severity patients with an AUC ranging between 0.73-0.92 across all levels of the ESI.

## 3 Objectives and Outcome Measures/Endpoints

### 3.1 Primary research question

Can ambulance service clinical data predict an avoidable attendance at the ED in adults using classification models?

#### 3.1.1 Primary objective

To build classification models deriving risk predictions using prehospital clinical data as input variables, and ED experience as the output variable.

#### 3.1.2 Primary outcome measure

An avoidable attendance at ED as defined by O’Keeffe et al. (2018).

### 3.2 Secondary research questions

What is the simulated transportability of the model derived from the primary outcome?

Which classification model is most accurate at predicting an avoidable attendance at the ED in adults?

#### 3.2.1 Secondary objectives

Internally validate the model and apply to a retrospective cohort of non-conveyed patients.

Compare the different classification models for most accurate and feasible to embed in practice.

#### 3.2.2 Secondary outcome measure

Avoidable attendance at ED as defined by O’Keeffe et al. (2018)

Comparative accuracy in prediction, misclassification rate, imprecision and inaccuracy.

## 4 Study Design

This prognostic study has a retrospective correlational design. Phase 1 will start by receiving a dataset of ambulance service journeys linked to ED records. This will be linked and anonymised externally by NHS digital (NHSD). Each patient episode in the dataset will contain clinical information from both the ambulance service and ED. This linked cohort will be known as Cohort 1. Any unlinked data will be returned for an assessment of selection bias.

Classification models will be applied to the dataset to predict an avoidable attendance at ED (primary outcome measure). Phase 1 will end when the models have been derived.

Phase 2 will use methods such as bootstrapping and cross-validation to internally validate the models. The models will also be applied to random samples of patients who were not conveyed to the ED. Phase 2 will end when the most accurate model has been identified and selected.

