## 7.3 Model Development

### 7.3.1 Data preparation and missing data for cohort 1

There will be an initial exploration to examine quantity of candidate variables within the dataset and the parameters within each one. This exploration will also identify missing data, and highlight any variables that may need cleaning or preparing in anticipation of model development. The outcome variable will be created using the variables derived from the ED data. Once created, the ED variables will be removed from the dataset. This completes the data preparation stage.

Any missing data will be assessed for randomness using statistical methods such as Little's Missing Completely at Random Test. If there is a small (<2%) of random data missing, then complete case deletion of the missing data will be considered. Alternatively, any arbitrary missing data will be handled with multiple imputations. Any monotonic pattern of missing data will be approached after further consultation with a statistician to prevent systematic bias entering into the models.

Following on from this, the cohort 1 sample will be compared to the unlinked data to assess for screening bias. Once this is complete, the unlinked data will be destroyed.

Predictive models will be developed and applied to the data independently. There will be a preference to use the whole dataset to derive each model and then use resampling techniques such as bootstrapping to measure optimism and recalibrate, (as opposed to sample splitting). For models which do require a training set and test set, this split will be done non-randomly, with the test data being unlabelled.

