### 7.4.4 Model selection

Once all adjusted models have been created and tested on cohort 2, there will be a comparative analysis of model performance using the same methods described above. The CI will then present the models to a small expert panel for independent confirmation. This panel will be a combination of clinicians and statisticians.

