## 8 Data Management

### 8.1 Data collection tools and source document identification

Yorkshire Ambulance Service has an ePCR system in place across the whole region. This is a compulsory system for paramedics to create and complete individual care records for each patient which begins at arrival on scene, and is completed once the patient is handed over. This document forms the source document for each patient that will be eligible in this project. The sample size in section 10.2 is in effect calculating the number of source documentation required for model derivation and validation.

Within each source document is the variables required to derive and validate the model. An example of the variables within can be seen in table 1 (above). The variables are mainly categorical and presented as drop down lists. The other type of variable captured is continuous such as age. The clinician is expected to fully complete each record however not all fields are compulsory capture.

This is a retrospective study and as such, there will be no attempt to maximise completeness of data. The sample size has been inflated to account for expected source document attrition at the point of data retrieval. The methodology has accounted for the handling of missing data.

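### The secondary objective asks for a model that is both accurate and feasible to use, but the outcomes and selection rule measure predictive performance only, on records whose gaps have been filled or removed

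*Protocol*

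**What the plan says.** **The objective.** Section 3.2.1, repeated in the summary table (section iii), reads: "Compare the different classification models for most accurate and feasible to embed in practice". It contains two criteria.

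**What follows from it.**
- The research question in 3.2 asks: "Which classification model is most accurate at predicting an avoidable attendance at the ED in adults".
- The outcome measure in 3.2.2 is: "Comparative accuracy in prediction, misclassification rate, imprecision and inaccuracy".
- Section 7.3.3 names sensitivity, specificity, predictive values, a calibration plot and the C-statistic.
- Section 7.4.4 says "there will be a comparative analysis of model performance using the same methods described above", after which an expert panel of clinicians and statisticians is asked to confirm independently.
- Section 4 closes the work: "Phase 2 will end when the most accurate model has been identified and selected".

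**The data on which models are compared.** Section 7.3.1 considers complete-case deletion if a small random amount (under 2%) is missing, and otherwise says: "Alternatively, any arbitrary missing data will be handled with multiple imputations". Monotone patterns are referred to a statistician. Section 7.4.2 treats cohort 2 in the same way.

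**The data a user would meet.** Section 8.1 says of the ambulance record: "The clinician is expected to fully complete each record however not all fields are compulsory capture". Section 11.1.1 foresees a toolkit that can be built into that record and used before the patient is transported.

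**The concern.** An objective with two criteria needs a measure for each. Feasibility has none, so the protocol as written can answer half of this objective and must leave the other half to impression. Section 11.1.1 also promises new knowledge on the feasibility of more complex models, and no planned analysis would supply it.

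The handling of missing data adds to this. A model that draws on many optional fields will more often meet a record it cannot score. If every model is assessed only after gaps have been imputed, or incomplete records dropped, that difference cannot be seen. Two models with the same C-statistic on completed data could differ materially in how often a crew could obtain a prediction, and the comparison would call them equal.

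**Working it through.** The main point is a comparison of sections and needs no arithmetic.

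| Place | Accuracy or performance | Feasibility |
|---|---|---|
| iii and 3.2.1, objective | yes | yes |
| 3.2, research question | yes | no |
| 3.2.2, outcome measures | yes | no |
| 7.3.3, statistics | yes (with calibration and discrimination) | no |
| 7.4.4, comparison | yes | no |
| 7.4.4, panel | confirmation, no criterion stated | no criterion or data |
| 4, end of Phase 2 | yes | no |

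Feasibility otherwise appears only as an expected product (11.1.1) and as something to be scoped during dissemination (11.2.2).

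**The second part is an inference in three steps.**
1. Under 7.3.1, each main route (imputation or deletion) yields records without gaps. Only monotone patterns are left open.
2. Under 8.1, some fields may be empty in real records.
3. Under 11.1.1, the tool is to work inside those records before transport. The protocol does not say how a record with an empty field would be scored, and plans no performance measure on records as captured.

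**Illustrative size.** The plan has no figure to reproduce here. The 7.7% in 7.2 concerns data for the outcome, not predictors.

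Inputs: 23 candidate fields (7.2 and 7.3.2). Assumptions: missingness *m* equal across fields and independent between them, and a 10-field comparator chosen only for contrast.

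Formula: share of records with all *k* fields present = (1 − *m*)^*k*.

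| *m* per field | *k* = 23 | *k* = 10 |
|---|---|---|
| 1% | 0.99^23 = 0.79 | 0.99^10 = 0.90 |
| 2% | 0.98^23 = 0.63 | 0.98^10 = 0.82 |
| 5% | 0.95^23 = 0.31 | 0.95^10 = 0.60 |

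The 2% row borrows the threshold in 7.3.1, read per field; that section does not say whether it applies per field or per record. Read per record, it would be met only if *m* were below 1 − 0.98^(1/23) = 0.09% per field, so imputation would then be the usual route.

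**The case against.** **Selection does not rest on the statistics alone.** Clinicians sit on the panel and may weigh usability. That is fair, but the panel's stated task is confirmation, and nothing tells it to consider feasibility or gives it material to do so.

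**A reader might infer that selection is biased towards the least usable model, or that a model with all 23 variables and 520 parameters would win on a trivial gain.** The protocol does not support this. Section 7.3.2 uses penalisation to remove weak predictors from the logistic model, and 7.4.3 plans optimism correction and cross-validation. The 520 is described in 7.2 as a generous count for sample size, not as the size of a final model. Nothing shows that the best validated model will need the most fields. What stands is that penalisation looks at effect on the outcome, not at how often a field is empty.

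**A reader might also suppose that the imputation uses the ED outcome.** No section says so, and cohort 2 has no outcome to use.

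**The illustration may exaggerate.** Several items in Table 1 are interventions, where a blank may mean not done. If gaps cluster in the same records, more records are complete than independence implies. Both points stand, and the percentages should not be read as estimates.

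**Deployment is later work.** Sections 11.1.1 and 11.2.4 put refinement, implementation and real-world testing after this study, and an unseen analysis plan may add detail. That limits how much can be asked now. It does not remove the mismatch, because this protocol makes feasibility part of its own objective and itself fixes the rule that ends Phase 2.

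**Missing data are already explored.** Sections 7.3.1 and 7.4.2 plan this for both cohorts. That is true, but it is not tied to any model or to selection.

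**Conclusion.** The point holds. The objective names feasibility; the research question, outcomes, comparison methods and end-of-phase rule do not, and the panel is given nothing with which to judge it. This rests on the text alone. Accuracy should be read broadly here, since calibration and discrimination are included.

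The missing-data part holds as an inference: performance is compared on imputed or complete-case records, while optional fields can be empty in use, so dependence on such fields does not enter the comparison. Its size cannot be stated from the protocol. The contrasts of 63% against 82% and 31% against 60% show only what independent, equal missingness of 2% and 5% would produce for 23 fields against an assumed 10.

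The documents do not establish a direction of bias in model selection. Nor do they justify a mandatory rule that the model with the highest scorable share must be chosen. How much performance to give up for usability is a judgement for the investigators and the panel, provided that both are in front of them.

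**What to change.** 1. **Add a feasibility measure to 3.2.2 and 7.4.4.** For each model, report the number of fields required and the proportion of episodes in cohort 1 and in cohort 2 that can be scored from fields as recorded. State for which fields a blank means not done. Note that 8.1 has the record completed at handover, so finished records may overstate what is available at the transport decision. Cohort 2 has no outcome and cannot inform accuracy, but it can inform this measure.
2. **Add a sensitivity analysis.** Report each model's optimism-corrected performance in cohort 1 with missing inputs handled in a way a live tool could apply, for example a not-recorded category or single values stored with the model.
3. **Amend section 4 and 7.4.4** so that selection and panel confirmation consider both performance and the feasibility results, and bring the research question in 3.2 into line with the objective.

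The cost is wording in four places, one tabulation per model built on the missing-data exploration already planned, and one further evaluation in cohort 1. The chosen model might perform marginally less well on imputed data than the most accurate one.
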